#### **4.3.1.8 Unknown Risks**

Furthermore, as with all research there is the remote possibility of risks that are unknown or that cannot be foreseen based on available information. This would include late effects that have been seen with some vaccines.

At the time of writing the protocol, the V920 study vaccine has been given to >20,000 participants in clinical trials in Africa. Serious adverse event reporting is monitored in real time in a blinded fashion. Un-blinded interim analyses have been performed in several trials.

#### **4.3.1.9 Risks to the Study Personnel and the Environment**

The principal risk for study personnel is exposure in the clinical setting to infectious pathogens from study subjects through various contact mechanisms (eg, needle stick exposure to blood borne pathogens and exposure to respiratory pathogens). There is also the theoretical risk of transmission of vaccine vector (rVSV) through exposure to shed vaccine in blood or body fluids. Adherence to routine practices and additional precautions and standard operating procedures (SOPs) for working with infectious agents will reduce the risk of exposure.

There are no known risks to the environment other than those associated with the generation of biohazardous waste attendant to vaccination of humans. All biohazardous waste will be disposed of as stipulated by local, state, and federal regulations and in accordance with study site SOPs.

Health Care Workers (HCW) were initially excluded and subsequently included in order to increase recruitment. During the original design of the trial HCWs were excluded because of the theoretical possibility that HIV infected persons would be more likely to shed vaccine vector following immunization due to their immune-compromise. Since that time accumulated evidence does show transient vector viremia but no evidence of transmission of the VSV vector. All study participants are given guidance about use of infection prevention and control measures and use of personal protective equipment to prevent sharing of secretions. It is anticipated therefore that the risk of a participant's VSV vector being transmitted to the persons they care for is very low. Health care workers are enrolled in other V920 studies and given guidance about infection prevention and control measures.

### 4.3.2 INTENDED BENEFIT FOR SUBJECTS

There is no intended direct benefit for study subjects. Subjects will receive a general health care screening as part of their participation in the study, and these results may be shared with their health care provider for their medical care, if permission of the participant is given. It is possible that vaccination with V920 may result in an immune response to Ebola virus. The protective efficacy of such a response is unknown.

Additional details regarding specific benefits and risks for subjects participating in this clinical trial may be found in the accompanying Investigators Brochure (IB) and Informed Consent documents.

## 5.0 METHODOLOGY

### 5.1 Entry Criteria

#### 5.1.1 Diagnosis/Condition for Entry into the Trial

Male/Female subjects with HIV-infection at least 13 years of age will be enrolled in this trial.

#### 5.1.2 Subject Inclusion Criteria

To be eligible for the study, each participant must satisfy ALL of the following criteria:

- 1) HIV-infected adult or adolescent male or non-pregnant, non-breastfeeding female, ages 13 to 70 (inclusive) at the time of screening;
- 2) On antiretroviral therapy with an undetectable viral load (< 40 c/ml);
- 3) CD4 T cell counts  $\geq 200$  cells/mm^3;
- 4) Written informed consent (subject or parent) and assent (adolescent), after reading the consent form and having adequate opportunity to discuss the study with an investigator or a qualified designee
- 5) Free of clinically significant health problems that could affect the safety of the participant, as determined by the Investigator by pertinent medical history and clinical examination prior to entry into the study;
- 6) Available, able, and willing to participate for all study visits and procedures;
- 7) Males and females who are willing to practice abstinence from sexual intercourse, or are willing to use effective methods of contraception, from at least 30 days prior to vaccination until 2 months after vaccination.
  - a. If the partner is NOT of childbearing potential, the couple will only be required to use condoms, without other adjunctive contraception.
  - b. For this study, a woman is considered of childbearing potential unless postmenopausal ( $\geq 1$  year without menses) or surgically sterilized (tubal ligation, bilateral oophorectomy, or hysterectomy)
  - c. Effective contraception is defined as a contraceptive method with failure rate of less than 1% per year when used consistently and correctly and when applicable, in accordance with the product label for example:
    - i. Male condoms PLUS:

- ii. Oral contraceptives, either combined or progestogen alone
- iii. injectable progestogen
- iv. implants of etenogestrel or levonorgestrel
- v. oestrogenic vaginal ring
- vi. percutaneous contraceptive patches
- vii. intrauterine device or intrauterine system

8) Be willing to minimize blood and body fluid exposure of others for 8 weeks after vaccination

- a. Avoiding the sharing of needles, razors, or toothbrushes
- b. Avoiding open-mouth kissing

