#### **4.3.1.4 Pregnancy**

Risks from the study vaccines to human fetuses are unknown at this time. As such, pregnant females will be excluded from participation. All female subjects of childbearing potential must be abstinent from intercourse with a male partner or utilize effective contraceptive precautions, as defined in the inclusion criteria (section 8.4), from 30 days prior to the date of vaccination through 2 months after the last vaccination. Non-childbearing potential is defined as either surgically sterilized or one year post-menopausal (defined as 12 consecutive months without menses).

Given the theoretical risk of transmission to a female partner of child bearing potential, male subjects will also be required to utilize effective contraception precautions for the same period of time.

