##### **7.1.5.1 Screening**

Approximately 30 days prior to treatment allocation/randomization, potential subjects will be evaluated to determine that they fulfill the entry requirements as set forth in Section 5.1. To exclude transient laboratory abnormalities, the investigator may repeat a test once during the screening period (ie a maximum of two tests), and if the repeat test is normal, subject may be enrolled. If the screening period for a particular study cohort has elapsed, a participant who was not eligible for an earlier cohort may be screened for eligibility for a later cohort.

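### Criterion 7a ties the condom-only exemption to the partner alone, so a fertile female participant with a male partner literally needs only condoms, contrary to Section 4.3.1.4

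*Combined protocol and SAP*

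**What the plan says.** Criterion 7 in Section 5.1.2 asks male and female participants to abstain or use effective contraception around vaccination. Three sub-items qualify it:

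- 7a gives an exemption: "If the partner is NOT of childbearing potential, the couple will only be required to use condoms, without other adjunctive contraception".
- 7b supplies the definition: "a woman is considered of childbearing potential unless postmenopausal" or surgically sterilised.
- 7c sets the standard: "Effective contraception is defined as a contraceptive method with failure rate of less than 1% per year when used consistently and correctly". Its example list opens with "Male condoms PLUS" and then names hormonal and intrauterine methods.

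Section 4.3.1.4 states the rule for women separately: "All female subjects of childbearing potential must be abstinent from intercourse with a male partner or utilize effective contraceptive precautions". For what counts as effective, it sends the reader to the inclusion criteria but places them in section 8.4. The period it sets runs "from 30 days prior to the date of vaccination through 2 months after the last vaccination". The same section says the risk to the fetus is unknown. It extends contraception to male participants because vaccine virus might, in theory, pass to a female partner who could conceive.

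On eligibility, Section 7.1.5.1 says that "potential subjects will be evaluated to determine that they fulfill the entry requirements as set forth in Section 5.1". Section 7.1.1.2 has the site review the full set of criteria, and Section 7.1.2 has them reviewed again at Visit 1.

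**The concern.** An exemption based on the partner's fertility suits a male participant, since the pregnancy at risk would be his partner's. For a female participant the pregnancy at risk is her own, and 7a does not ask about her status. Because 7b attaches childbearing potential to women only, a male partner can never have it. The exemption is therefore open to every female participant with a male partner, including one who could conceive.

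This also reverses the order of risk. The unvaccinated female partner of a male participant, exposed only through theoretical transmission, gets the full contraceptive standard. A woman injected with the live vaccine herself gets condoms alone.

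What is at stake is protection of participants and any fetus. No estimate, test or sample-size figure depends on it.

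**Working it through.** The protocol gives no figure to reproduce. The check applies the literal text of 7, 7a, 7b and 7c to each type of couple and compares the result with Section 4.3.1.4.

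| Participant | Partner | Partner of childbearing potential under 7b? | Literal requirement | Agrees with 4.3.1.4? |
|---|---|---|---|---|
| Male | Fertile female | Yes | Full 7c standard | Yes |
| Male | Non-fertile female | No | Condoms only | Yes, as intended |
| Fertile female | Male | No, defined for women only | Condoms only | **No** |
| Non-fertile female | Male | No | Condoms only | Yes, harmless |

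Only the third row fails. Section 4.3.1.4 takes its definition of effective precautions from the inclusion criteria, and the only definition there is 7c. Condoms alone do not appear in that list; they appear only with a second method. So 7a asks less of this woman than 4.3.1.4 does. As an exception to 7c, 7a is legitimate in form. The conflict is with 4.3.1.4, with 7c supplying the standard that 4.3.1.4 uses.

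Two pieces of context follow. Neither measures the gap, because both are the same under either reading of 7a.

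*Contraception window under 4.3.1.4, taking 2 months as 60 days (61 in brackets):*

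- Cohorts 1–4: 30 + 60 = 90 days (30 + 61 = 91).
- Cohort 5, second dose at Day 56: 30 + 56 + 60 = 146 days (30 + 56 + 61 = 147).

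*Scheduled urine pregnancy tests in the Section 6.0 flow charts:*

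- Cohorts 1–4: screening and Day 0, so 2.
- Cohort 5: screening, Day 0 and Day 56, so 3.
- After the last dose: 0 in both, leaving about 60 days of the window without a scheduled test.

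**The case against.** **Section 4.3.1.4 has no standard of its own.** It borrows from the inclusion criteria, so it arguably borrows 7a as well, and then nothing conflicts. This does not succeed. 7a is an exemption, while 4.3.1.4 refers to a definition, which is 7c. If 7a were imported, no female participant with a male partner would ever be held to 7c, and the sentence in 4.3.1.4 covering all women of childbearing potential would have no effect.

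**The literal reading defeats itself.** An exception should not cancel its own rule, so a sensible reader would take 7a to apply only where nobody in the couple can conceive. That is probably the intent, and the main clause and 7c sit beside 7a for the site to see. This part stands: the intended rule can be inferred. But an eligibility criterion applied at four sites in three countries should state its rule, and the clear statement sits in the risk background with a wrong pointer to the criteria.

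**The remedy may create a new ambiguity about a sterile male partner.** It need not. The methods in 7c are examples, so a sterile partner can be judged against the below-1% standard.

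**The effect is small.** This also stands. Condoms remain required, exclusion 13 in Section 5.1.3 bars women who are pregnant or intend to be, and tests fall at screening and on each dosing day. These safeguards narrow the gap without closing it, since none of them supplies the second method that 7c calls for against unintended conception. The lack of a scheduled test after the last dose is a separate matter that the correction leaves as it is.

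**Conclusion.** The point holds. As written, 7a lets a female participant of childbearing potential with a male partner enter on condoms alone, which is less than Section 4.3.1.4 requires. The conclusion rests on the literal wording of 7a and 7b and on reading 7c as the definition that 4.3.1.4 refers to.

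This is a wording inconsistency in an operative eligibility rule, with a modest practical effect and no statistical consequence. The number of women concerned cannot be derived from the documents. It should be fixed because fetal risk is unknown for a live vaccine and the repair costs almost nothing. The wrong cross-reference in 4.3.1.4 is clerical and would not merit a point by itself.

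**What to change.** Add one sentence to 7a and leave the rest as it is:

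> This exemption does not apply to a female participant of childbearing potential (7b) who has a male partner; she must abstain or use effective contraception as defined in 7c.

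This changes only the failing row of the table. The rules for male participants, for women who cannot conceive and for same-sex couples are untouched, so the wording remains inclusive.

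In Section 4.3.1.4, change the reference from section 8.4 to 5.1.2. Align any eligibility checklist or consent text that repeats 7a.

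The cost is one sentence, one corrected reference and those alignments. Any woman already enrolled on condoms alone would need her contraceptive method re-checked; the documents do not show whether there are any.

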### 5.1.3 Subject Exclusion Criteria

Participants with any of the following criteria will be excluded:

1. History of prior infection with a filovirus or prior participation in a filovirus vaccine trial;
2. History of prior infection with VSV or receipt of a VSV-vectored vaccine;
3. Presence of any febrile illness or any known or suspected acute illness on the day of any first immunization (subject may be rescheduled);
4. Clinical manifestations of systemic diseases considered by the investigator to impact safety or immunogenicity
5. Receipt of systemic glucocorticoids (a dose  $\geq$  20 mg/day prednisone or equivalent) within one month, or any other cytotoxic or immunosuppressive drug within 12 months;
6. Receipt of any investigational drug within 12 months of vaccination;
7. Receipt of any live virus vaccine within 42 days prior to study entry or any other (non-live virus) vaccine within 14 days prior to study entry.
8. History of sensitivity to any component of study vaccines per investigator brochure or package insert;

**Any baseline laboratory screening tests which is outside of acceptable range as defined in the protocol (local site reference ranges): ALT, AST, creatinine, hemoglobin, platelet count, total white blood cell count, urine protein, urine occult blood, urine glucose AND considered clinically significant by the clinical investigator. The following five screening parameters have limits set:**

- a. absolute lymphocyte count  $\geq$ 1000 cells/mm^3
- b. hemoglobin not greater than 1.5 grams below the lower limit of the normal reference range at the local laboratory
- c. ALT, AST not greater than 2 to 2.5 times the upper limit at the local laboratory

- d. Platelet count  $\geq 125,000$  and  $\leq 550,000$
- 9. To exclude transient laboratory abnormalities, the investigator may repeat a specific test (E.g. hemoglobin) once during the screening period (I.e. a maximum of two tests), , and if the repeat test is normal, subject may be enrolled;
- 10. Have an active malignancy or history of metastatic or hematologic malignancy except non-melanoma skin cancers;
- 11. Suspected or known alcohol and/or illicit drug abuse within the past 5 years;
- 12. Moderate or severe illness and/or fever  $>101^{\circ}\text{F}$  ( $38.3^{\circ}\text{C}$ ) orally or  $> 100^{\circ}\text{F}$  ( $37.8^{\circ}\text{C}$ ) axillary within one week prior to vaccination;
- 13. Pregnant or breastfeeding female, or female who intends to become pregnant during the study period;
- 14. Administration of immunoglobulins and/or any blood products within the 120 days preceding study entry or planned administration during the study period;
- 15. Any other significant finding that in the opinion of the investigator would increase the risk of the individual having an adverse outcome from participating in this study.

## 5.2 Trial Vaccination

The vaccines to be used in this trial are outlined below in Table 2:

Table 2: Trial Treatment/Vaccination

Vaccine	Dose/Potency	Dose Frequency	Route of Administration	Regimen/Treatment Period/Vaccination Regimen	Use
V920	$\geq 2 \times 10^7$ PFU in 1mL	Once in cohorts 1-4/Twice in Cohort 5	IM	Visit 1, D0 and Visit 7 (Day 56), where applicable	Experimental
Normal saline (0.9%)	1 ml	Once in cohorts 1-4/Twice in Cohort 5	IM	Visit 1, D0 and Visit 7 (Day 56), where applicable	Placebo-control
Subjects in Cohort 5 will receive two doses of V920 $\geq 2 \times 10^7$ PFU or two doses of normal saline placebo (0.9%) on D0 and D56.					

Vaccination is given on the day of treatment allocation/randomization or as close as possible to the date on which the subject is allocated/assigned.

The vaccine dose will be administered at the trial site at Visit 1 (and Visit 7 for Cohort 5). Participants will be observed 30 minutes after vaccination to monitor for immediate hypersensitivity reactions.

All products indicated in Table above will be provided centrally by the Manufacturer or locally by the trial site, subsidiary or designee, depending on local country operational or regulatory requirements.

For any commercially available product that is provided by the trial site, subsidiary or designee every attempt will be made to source these supplies from a single lot/batch number. The trial site is responsible for recording the lot number, manufacturer, and expiry date for any locally purchased product as per local guidelines unless otherwise instructed by the Sponsor.

The investigator shall take responsibility for and shall take all steps to maintain appropriate records and ensure appropriate supply, storage, handling, distribution and usage of trial treatments in accordance with the protocol and any applicable laws and regulations.

### **5.2.1 Formulation, Packaging, and Labeling of V920**

The rVSVΔG-ZEBOV-GP vaccine (V920) consists of a single recombinant VSV isolate modified to replace the gene encoding the G envelope glycoprotein with the gene encoding the envelope glycoprotein from Ebola virus-Zaire.

The vaccine product is supplied in a sterile 1.0-mL vials. Each vial contains vaccine virus frozen in a mixture of 10mM Tris, pH 7.2 and recombinant human serum albumin 2.5 mg/mL. After thawing, the content of the vials is a clear liquid. The vaccine concentration in the vial is titered to at least  $2 \times 10^7$  pfu/mL (stock).

### **5.2.2 Storage and Stability**

rVSVΔG-ZEBOV-GP vaccine product (V920) is to be stored at or below -60°C for long-term storage. Storage temperature will be continuously monitored and recorded. Vaccine product will be stored in a locked room with access restricted to only necessary study site personnel. Vaccine should be stored and transported at temperatures at or below -60°C.

Normal saline (0.9%) should be stored according to its labeling.

### **5.2.3 Preparation, Administration, and Dosage of V920**

rVSVΔG-ZEBOV-GP vaccine (V920) will be administered as an IM injection. V920 should be removed from the freezer and thawed at room temperature (not 2-8°C) for approximately 10-15 minutes. The thawed vial should then be gently inverted several times prior to withdrawal with the syringe. The study vaccine is considered to be thawed when there is no visible ice on the outside of the vial. The study vaccine should appear as a colorless liquid with no particulates visible. If the study vaccine appears cloudy or has particulates, a replacement vial should be assigned and administered. Once thawed in the clinic, a total cumulative of 15 minutes at 25°C and/or 27 days at 2-8°C is permitted. Refreezing is not permitted by the end user. The formulation and/or image of the study vaccine and placebo control may appear

different. Therefore, an unblinded pharmacist (or other designated unblinded person) at the site will be required to prepare the study vaccine/placebo in order to maintain the blinding. The unblinded personnel will not participate in post-vaccination assessments. Both study vaccine and placebo are clear, and indistinguishable from one another once in the syringe. Once the syringe is prepared, the blinded personnel will administer the study vaccine/placebo to the subject. If V920 is administered, a dose of  $2 \times 10^7$  pfu/mL will be given in a 1mL volume. Prior to injection, the area to be injected will be cleaned with an alcohol swab. 1.0 mL of study vaccine/placebo should be administered intramuscularly (IM) in the deltoid muscle of the non-dominant arm at a 90° angle into the muscle tissue, using a needle long enough to ensure IM deposition of the study vaccine/placebo. A 1-inch #23-gauge needle is recommended. The vaccination arm must be recorded on the appropriate case report form for future reference in the event of potential injection-site reaction(s). Emergency medical supplies including epinephrine and advanced airway support will be available in case of serious allergic reaction.

#### **5.2.4 Dose Selection/Modification**

##### **5.2.4.1 Dose Selection (Preparation)**

The rationale for selection of doses to be used in this trial is provided in Section 4.0 – Background & Rationale. There are no specific calculations or evaluations required to be performed in order to administer the proper dose to each subject.

#### **5.2.5 Timing of Dose Administration**

All subjects will receive on D0 either the V920 (rVSVΔG-ZEBOV-GP) vaccine at a dose of  $\geq 2 \times 10^7$  PFU in 1mL IM, or normal saline (0.9%) placebo control in 1mL volume. Subjects in Cohort 5 will also receive on D56 a matching dose of either the V920 at a dose of  $\geq 2 \times 10^7$  PFU in 1mL IM, or normal saline (0.9%) placebo control in 1mL volume.

#### **5.2.6 Trial Blinding**

This is a double-blind trial; therefore, the Sponsor, investigator, and subject will not know the vaccine administered until unblinding.

### **5.3 Randomization or Treatment Allocation or Vaccine Allocation**

Subjects will be assigned randomly according to a computer-generated allocation schedule. Participants will be randomized 4:1 (study vaccine: placebo control) using centralized randomization, with a total of approximately -200 study vaccine recipients and 50 placebo control recipients. Treatments will be stratified as described below.

### **5.4 Stratification**

To satisfy the requirement that each site enrolls at least one placebo subject in each cohort, enrollment will proceed until treatments have been randomized to at least one complete block of subjects (consisting of four subjects receiving treatment and one receiving placebo) at each site.

Treatment allocation/randomization will be stratified by the 5 cohort groups:

- Cohort 1: Screening CD4 cell counts for adults: CD4 cells/mm^3  $\geq 500$
- Cohort 2: Screening CD4 cell counts for adults: CD4 cells/mm^3  $>350$  and  $< 500$
- Cohort 3: Screening CD4 cell counts for adults: CD4 cells/mm^3  $\geq 200$  and  $\leq 350$
- Cohort 4: Screening CD4 cell counts for adolescents, age 13 to 17: CD4 cells/mm^3  $\geq 200$
- Cohort 5: Screening CD4 cell counts for adults and adolescents, age 13 to 17: CD4 cells/mm^3  $\geq 200$  with 2 doses.

All sites are stratified by site (two sites per cohort).

Cohort 5 is stratified by site, and by age group (adolescent vs. adult). Once three blocks of five adolescents have been enrolled, with at least one block at each site, the requirement to enroll at least 12 adolescents in Cohort 5 will be met.

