#### 4.3.1.3 Reactions to V920

Detailed safety data collected in the Phase 2 and 3 studies to date have demonstrated V920 to be generally well-tolerated when administered to healthy, non-pregnant, adults. Injection site reactions following vaccination are generally mild to moderate and self-limited. Thereafter, there is a predictable period of early reactogenicity, including fever and a flu-like syndrome and resolves with 7 days. During this time, transient decreases in white blood cells and platelets

have also been observed but bleeding or increased risk of infection has not been reported. The early reactogenicity is likely to be a result of viremia with the vaccine virus which resolves within 2 weeks. Vaccine virus has been found in saliva, urine, and skin-vesicles in vaccines. Person-to-person transmission has not been documented, however transmission through shedding and close personal contact is accepted as a theoretical possibility. Joint pain (arthralgia) is part of the early flu-like syndrome in the first week after vaccination in up to 44% of vaccines. In a small proportion of subjects (<5%), joint swelling (arthritis) may develop in the 2nd to 3rd week after vaccination. The arthritis is thought to be virally-mediated, and while the majority of arthralgia and arthritis events resolved spontaneously, recurrent or persistent arthralgia and arthritis have also been reported. The safety profile reported from the Ebola-epidemic region has been similar to that observed outside the region.

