## 9.3 Clinical Supplies Disclosure

This trial is blinded but provided open label; therefore, an unblinded pharmacist or qualified trial site personnel will be used to prepare the vaccine. Both study vaccine and placebo are clear, and indistinguishable from one another once in the syringe. Once the syringe is prepared, blinded personnel will administer the 1.0 ml study vaccine or placebo control to the subject.

Vaccine identification information is to be unmasked ONLY if necessary for the welfare of the subject. Every effort should be made not to unblind the subject unless necessary.

In the event that unblinding has occurred, the circumstances around the unblinding (e.g., date and reason) must be documented promptly, and the Medical Monitor notified as soon as possible. Only the principal investigator or delegate and the respective subject's code should be unblinded. Trial site personnel and Sponsor personnel directly associated with the conduct of the trial should not be unblinded.

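### Section 5.4 shows sites a block of five with one placebo, and the unblinded preparer is not barred from enrolment; that person could know about 44% of assignments in advance

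*Combined protocol and SAP*

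**What the plan says.** **Blocks.** Section 5.4 requires each site to enrol at least one placebo subject in each cohort. It secures this by continuing until randomisation has filled "at least one complete block of subjects (consisting of four subjects receiving treatment and one receiving placebo) at each site". For the adolescents in Cohort 5 it adds: "Once three blocks of five adolescents have been enrolled, with at least one block at each site". Five is the only block size mentioned, and nothing is said about varying or concealing it.

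**Strata.** "Treatment allocation/randomization will be stratified by the 5 cohort groups". Section 5.4 continues "All sites are stratified by site (two sites per cohort"), and then "Cohort 5 is stratified by site, and by age group (adolescent vs. adult"). Section 5.3 specifies a computer-generated schedule, central randomisation and a 4:1 ratio.

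**The preparer.** Section 9.3 says: "This trial is blinded but provided open label; therefore, an unblinded pharmacist or qualified trial site personnel will be used to prepare the vaccine". Section 5.2.3 sets one limit on this role: "The unblinded personnel will not participate in post-vaccination assessments". It does not mention screening, consent or the timing of randomisation.

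**Unblinding.** Section 7.1.4.3 lets the investigator authorise emergency unblinding of a participant. Under section 9.3 the code then goes to the principal investigator or a delegate.

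**The concern.** A site knows its own enrolment order within each stratum. With the block size and composition printed in the protocol, it can count where each block begins and ends. Central randomisation hides the list, but not a pattern that the protocol discloses.

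The preparer sees each assignment. Once a block's single placebo has been prepared, the rest of that block must be V920. If the first four are V920, the fifth must be placebo. A person with this knowledge who also had a hand in enrolment could influence who is randomised next.

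The endpoints that depend on the blind are the solicited events recorded by subjects and the vaccine-related SAEs, both primary in section 4.2.3.2. Causality is an investigator's judgement (section 7.2.5). Table 4 makes exposure to the test vaccine one of its components, and lists not having received the vaccine as grounds for judging an event unrelated. The holds in Appendix 3 for death, life-threatening events and SAEs also turn on relatedness. Each cohort has only about 10 placebo subjects, so a few compromised assignments would count.

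**Working it through.** **1. Inputs.** Block of 5 with 4 V920 and 1 placebo; strata of cohort by site, plus age group in Cohort 5 (all section 5.4). About 250 subjects (section 1.0). The documents give no figure for predictability.

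**2. The plan's own totals.** 250 / 5 = 50 blocks, giving 50 × 4 = 200 V920 and 50 × 1 = 50 placebo, as in section 5.3. A cohort of 50 gives 10 blocks and 40:10, as in section 8.1. Three blocks of five are 15 adolescents (12 V920, 3 placebo), which meets the stated minimum of 12 adolescents. Blocks of five therefore fit every total in the plan.

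**3. Assignments certain in advance.** The five placebo positions are equally likely. For someone who sees every earlier assignment in the block:

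| Placebo position | Certain V920 | Certain placebo | Total certain |
|---|---|---|---|
| 1 | 4 | 0 | 4 |
| 2 | 3 | 0 | 3 |
| 3 | 2 | 0 | 2 |
| 4 | 1 | 0 | 1 |
| 5 | 0 | 1 | 1 |
| Sum, of 25 | 10 | 1 | 11 |

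The share is 11/25 = 44%: 40 points certain V920 and 4 points certain placebo. One of the five placebo assignments (20%) is known beforehand. Simulated strata of 25 and 50 subjects also give 44.0%. In a cohort of 50 the expected number is 0.44 × 50 = 22 assignments, 20 of them V920 and 2 placebo.

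**4. One emergency unblinding.**
- A placebo subject: the other four are V920 with probability 1, up from 0.80.
- A V920 subject: the one placebo is among the other four, so each one's placebo chance moves only from 1/5 = 20% to 1/4 = 25%.

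**5. Other block schemes, same observer.**
- Fixed blocks of 10 (8:2): 13/45 = 28.9% certain.
- Blocks of 5 and 10 in random order, assumed equally likely, with the observer knowing both sizes: about 10% by simulation (10.0% with 25 subjects per stratum, 10.5% with 50).

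**6. Effect of larger blocks on the one-placebo requirement.** If a stratum opens with a block of 10 and enrols only five subjects, P(no placebo) = C(8,5)/C(10,5) = 56/252 = 22%. A block of 10 holds 8 V920, so a placebo is guaranteed only from the ninth subject. Fifteen Cohort 5 adolescents over two sites, with at least one block at each, could mean 10 at one site and 5 at the other.

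**The case against.** The strongest reply is that the 44% describes someone who is unblinded by design and kept away from the endpoints. The investigator is blinded (section 5.2.6). Consent and eligibility rest with the investigator or a qualified designee (sections 7.1.1.1 and 7.1.1.2), causality with an investigator-physician, and injection with blinded staff using indistinguishable syringes. Selection would need the preparer to act as that designee or to pass assignments on. This is fair: no section provides for either. But no section forbids the preparer a role in enrolment, and that gap stands.

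It is also fair that fixed blocks are an inference. The schedule is not in the documents, and section 5.4 does not say that every block in every stratum has five subjects.

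Four stronger readings are tempting but unsupported:
- **One placebo per site and cohort.** Section 5.4 sets a minimum of one. The single placebo is per block, and a cohort of 50 has about 10.
- **Blinded staff can work out the placebo from reactions.** Section 4.3.1.3 says: "Joint pain (arthralgia) is part of the early flu-like syndrome in the first week after vaccination in up to 44% of vaccines". For a given subject, the chance that all four others in the block report arthralgia is 0.2 × 0.44^4 + 0.8 × 0.44^3 × q. That is 1.1% to 2.1% for an assumed placebo rate q of 5% to 20%. Such a pattern is rare, and reactions can hint at assignment whatever the block size.
- **The primary immunogenicity result is compromised.** GP-ELISA titre is a laboratory measure. Laboratory abnormalities, also a primary safety endpoint, are similarly less exposed.
- **Bias has occurred.** The documents show an opportunity only. Emergency unblinding should be rare, and about 80% of subjects received V920, for whom it reveals little.

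**Conclusion.** The point holds as a weakness in allocation concealment that should be corrected. The protocol discloses block size and composition to sites and leaves the unblinded preparer free, on paper, to take part in enrolment. For a preparer who sees every assignment in a stratum, an expected 44% of assignments, and 20% of placebo assignments, are certain in advance. This assumes fixed, complete blocks of five; a preparer who sees only some assignments would know less. Unblinding a placebo subject reveals four others, provided the enrolment order within the stratum is known, as it is at the site. The exposure is limited to selection at enrolment, subject-reported safety events and causality judgements. The size of any resulting bias cannot be estimated from the documents.

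**What to change.** 1. Remove block size and composition from section 5.4, including the sentence on adolescent blocks, and hold them in a document restricted to the unblinded randomisation statistician.
2. State the requirements as counts, monitored centrally: at least one placebo subject per site per cohort, and at least 12 adolescents in Cohort 5.
3. Extend sections 5.2.3 and 9.3 so that unblinded preparers take no part in screening, consent or the timing of randomisation.
4. For subjects not yet randomised, vary block size at 4:1 only in strata large enough to keep the one-placebo requirement. With blocks of 5 and 10 that means at least nine subjects expected. Do not do so in very small strata such as Cohort 5 adolescents, where items 1 and 3 carry the protection.

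**Cost.** A wording amendment, a regenerated schedule for the remaining subjects, and some central monitoring. An incomplete block of 10 can leave a stratum slightly off exact 4:1. Sites have already read the block size, so item 1 alone does not undo the disclosure. The documents do not say how many subjects remain to be randomised. If enrolment is complete, the sponsor can still record who prepared doses, what other trial tasks they had, and any individual unblinding.
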